## **Abbreviations**

ACH	Arkansas Children's Hospital
ACMEGS	American Clinical Magnetoencephalography Society
AE	Adverse Event
AEF	Auditory Evoked Field
APR	Annual Progress Report
CFR	Code of Federal Regulations
CRF	Case Report Form
CT	Computerized Tomography
dB	Decibel
DOB	Date of Birth
ECD	Equivalent Current Dipole
ECG	Electrocardiogram
EEG	Electroencephalography
EOG	Electrooculogram
ERF	Evoked Response Field
FDA	US Food and Drug Administration
fMRI	Functional Magnetic Resonance Imaging
HIPAA	Health Insurance Portability and Accountability Act
HPI	Head Position Indicator
kHz	Kilo Hertz
IAT	Intracarotid Amobarbital Test
ICF	Informed Consent Form
ICH GCP	International Council for Harmonisation Good Clinical Practice
IIR	Infinite Impulse Response
IRB	Institutional Review Board
ISI	Inter-Stimulus Interval
LCD	Liquid Crystal Display
MEG	Magnetoencephalography
MRI	Magnetic Resonance Imaging
MRN	Medical Record Number
MSR	Magnetically Shielded Room
nAm	NanoAmpere-Meter
msec	Millisecond
ORRA	Office of Research Regulatory Affairs
PET	Positron Emission Tomography
PI	Principal Investigator
s	second
SAE	Serious Adverse Event
SD	Standard Deviation
sLORETA	Standardized Low Resolution Brain Electromagnetic Tomography
SPL	Sound Pressure Level
SQUIDs	Superconducting Quantum Interference Devices
SSP	Signal-Space Projection
UADE	Unanticipated Adverse Device Effect
UAMS	University of Arkansas for Medical Sciences
UPIRTSO	Unanticipated Problem Involving Risks to Subjects or Others
VSWM	Visuospatial Working Memory
WM	Working Memory

Title: Pediatric Language and Memory Mapping in Refractory Epilepsy using Magnetoencephalography

PI: [name]

Site: Arkansas Children's Hospital

## **Background and Rationale**

Pediatric epilepsy is the most common serious neurological disorder of childhood, affecting between 0.5-1% of children and young people under the age of 16 years [1]. Epilepsy is known to impair behavior, and adversely affect cognition and learning [2-4]. Antiepileptic drugs are effective medications available for epilepsy. However, many patients do not respond to this treatment and become resistant. Treatments such as the ketogenic diet, vagal nerve stimulators and resective and functional surgery have become available for these drug-resistant patients [5]. Surgery for removal of epileptogenic zone is the most effective treatment. The purpose of presurgical brain mapping is to facilitate surgical planning, prevent or reduce morbidity, and optimize the therapeutic effects of surgery. As part of the presurgical planning, assessment of hemispheric language and memory function is performed. The medical standard for determining the language dominant hemisphere and memory function prior to surgical resection is the intracarotid amobarbital test (IAT), also known as the Wada test [6]. It consists of an injection of sodium amobarbital into the left or right internal carotid arteries. This causes a temporary arrest of function in each hemisphere for approximately six to ten minutes, during which the unanaesthetised hemisphere is functionally assessed. A major drawback of this test is that it determines lateralization only, and does not allow intrahemispheric localization of language and memory functions. Moreover, because it is relatively invasive, this technique cannot be used with normal volunteers and is difficult to use with children. Additionally, the Wada test is associated with risks of stroke, infection, and hemorrhage [7]. Over the past decade, there is a significant discussion of the clinical utility of non-invasive brain imaging techniques (e.g. functional magnetic resonance imaging (fMRI)/ magnetoencephalography (MEG)) relative to the invasive Wada test for determination of hemispheric language and memory function. At present, while research has pointed to the better spatiotemporal resolution of both behavior and functional brain network organization available in brain imaging methods, the lack of language and memory tasks that map these functions in single individuals has reduced their clinical utility. The impact of epilepsy on language and memory are relevant not only from a clinical perspective but also because it sheds light on the underlying neurobiology of both processes. Identifying the patterns of language and memory organization prior to surgical intervention could therefore guide tailored resection and limit potential loss of function after surgery.

Advances in technology over the past decade have enabled researchers to study the functional development of the human brain with MEG, a novel and non-invasive technique with fine temporal and spatial resolution. While other modalities infer brain function indirectly (i.e. positron emission tomography (PET), computerized tomography (CT), MRI) by measuring changes in blood flow, cerebral metabolism and blood oxygenation, MEG records neuronal and synaptic function directly. MEG records the tiny biomagnetic fields generated by ionic currents generated by populations of synchronously activated neurons in the brain [8]. Evoked responses fields (ERF) measured with MEG, much like event-related potentials in electroencephalogram (EEG), are waveforms representing variations of brain activity across time following the onset of an external stimulus (auditory, visual, etc.). Early components of the ERF waveform (150-200 msec after stimulus onset) reflect neurophysiological activity in primary sensory cortices. On the other hand, neurophysiological activity represented by later components of the ERF waveform occurs primarily in association cortices. By estimating the regions that contribute to systematic variations in the late components of the ERF, we can study the brain circuits responsible for cognitive and linguistic functions. MEG signal arises from brain sources also seen using electrical signals recorded as the EEG. However, MEG is unaffected by scalp, skin and, to a large degree, brain tissue in homogeneities and is, therefore, an ideal technology to study brain development. MEG is one of several diagnostic techniques employed for the evaluation of patients with epilepsy and it is especially important for those patients being considered for epilepsy surgery [9, 10]. Resective

Title: Pediatric Language and Memory Mapping in Refractory Epilepsy using Magnetoencephalography

PI: [name]

Site: Arkansas Children's Hospital

epilepsy surgery is performed mainly in the temporal and frontal lobes (selective amygdalohippocampectomies, anterior temporal lobectomies, or tailored temporal or frontal corticectomies). However, it must be previously determined that the resection will not have any substantial consequences on cognitive functions, such as language or memory.

fMRI is the most widely used of the minimally/non-invasive techniques for presurgical language mapping in children [11]. However, MEG is gaining increasing acceptance as a non-invasive method as an adjunctive part of the pre-surgical functional mapping procedure [12]. Especially for language identification in pediatric cases, the quiet environment of the MEG room and the head-motion-tracking methods available in recent MEG systems, increase the likelihood of success with language lateralization in young populations. Further, MEG allows examining both hemispheres simultaneously, which is especially useful in epileptic populations, in which language lateralization is more variable. MEG language localization studies have shown encouraging results with a wide variety of paradigms, especially in localization of receptive language areas that are well documented [13, 14] and validated [15, 16]. The suitability of MEG language lateralization protocols in adults as an alternative to the Wada procedure have been addressed with validation studies conducted using various methodologies and exhibit overall high concordance rates (about 86-92%) [17-20]. Language lateralization is calculated in both hemispheres by localizing dipole sources (equivalent current dipole, ECD model) accounting for late auditory evoked field (AEF) components (150-700 ms after stimulus onset). These late components localize to language-related areas (mainly within posterior temporal areas) of the brain regardless of the modality of stimulus presentation [21]. Depending on the activation task, the dipole sources can be used to identify the location of receptive (Wernicke's area) or expressive language-specific (Broca's area) cortex. The degree of hemispheric asymmetry in the duration or strength of activation can also be calculated as an index of hemispheric dominance for language functions. Estimations of language lateralization with MEG [22] have mainly been based on recognition memory tasks for spoken words [23] or by listening to synthesized vowel sounds [24]. Thus, most of the MEG language studies have focused on receptive language areas. However, other reports exist on frontal circuits in expressive language [25-27] and basal temporal areas during semantic language tasks (verb generation) [28, 29]. Recent MEG language studies have reported the feasibility of passive paradigms in children and adolescents under sedation [30] and during sleep [31]. A recent MEG study [32] uses a verbal memory and verbal fluency tasks showing activation of the left hippocampus and in Wernicke's area in favor of the left hemisphere. Authors found higher concordance rates between a verbal memory paradigm and language dominance in controls (using handedness as criterion) and in subjects with epilepsy (using fMRI or Wada as criterion), compared with a verbal fluency task. Only the concordance for verbal memory reached statistical significance, with 93% agreement. Previous studies in pediatric epilepsy have shown atypical language lateralization [33] and that the word recognition task is the only language comprehension task used in both children and adults that yields high concordance between MEG and the Wada test for language lateralization [22]. Despite all contributions of MEG in the assessment of language localization in typically developing individuals, studies in pediatric populations with epilepsy is still relatively small especially in single subjects, which is necessary for clinical utility.

Memory involves a network of interconnected anatomical brain structures - hippocampus, parahippocampal structures, temporal lobe neocortex, amygdala, and the frontal lobe [34, 35]. Medically intractable epilepsy may negatively affect cognition by disrupting cognitive processes through chronic and persistent seizures. Verbal memory declines in about 30-85% of epileptic patients undergoing left temporal lobe resection while non-verbal memory declines in about 30-50% of the patients when right temporal lobe resection is performed [36, 37]. The standard

Title: Pediatric Language and Memory Mapping in Refractory Epilepsy using Magnetoencephalography

PI: [name]

Site: Arkansas Children's Hospital

procedure used to assess the risk of resection-induced loss in memory function prior to epilepsy surgery is with the invasive Wada Test together with language assessment. fMRI has been used to assess the risk of memory loss in epilepsy [38]. Usually, fMRI studies perform language protocols to predict memory outcome. However, this approach assumes collateralization of these functions, which has previously been studied, but dissociating these domains of function can be difficult, partly due to reorganization, and to overlapping and/or interconnectivity of regions involved during cognitive processing. Very few MEG studies exist for memory assessment, and most of them have been performed in adult epileptic subjects [39, 40] and less in children. Currently, there are insufficient available data to promote the use of MEG for assessment of pediatric memory function, as memory function is housed deep in the temporal lobes and is more difficult to accurately localize. However, previous studies have shown that it is possible to detect hippocampal activity with MEG [41] that will allow the study of deep sources involved in memory.

Working memory (WM) and executive functions are skills developed to deal with complexities in life and are necessary for effective and adaptive behaviors. WM is the cognitive system that entails maintaining information in mind over a short time to complete an activity. WM is one of the most important components of information processing. A dysfunction of the WM system may lead to problems in developing cognitive functions, including mental arithmetic, reading, decision making and reasoning. WM is constituted by three main components: the central executive, the phonological loop, and the visuospatial sketch pad. Each component works to store and manipulate information in a temporary short-term memory system that is essential to human memory [42]. Executive functions include the control and organization of complex cognitive operations that allow a person to plan strategies, solve problems, and modify behaviors as a result of new information. The frontal lobes play a crucial role in WM and epilepsy has an impact on working memory functioning [43]. Visuospatial working memory (VSWM) involves encoding, maintenance, and retrieval of object identity, particularly spatial position [44-47]. VSWM is especially important in children during letter/number recognition, reading, writing, and math by facilitating recall of shapes and colors as well as their positions and movements. Determination of hemispheric memory lateralization plays an important role in the presurgical epilepsy evaluation, and very few studies have been conducted in children. The comparisons between adults and children revealed a greater activation in large regions of the frontal, parietal and temporal lobes, basal ganglia, and cerebellum in adults, while children showed greater activity in several occipital regions [48]. In adults, verbal memory has been predominantly lateralized over the left temporal lobe and visual-spatial memory over the right hemisphere [49-51]. But in children with epilepsy, a clear pattern of hemispheric lateralization of visuospatial memory has not been thoroughly investigated and established, and more investigations are needed to further assess WM in epilepsy.

How epilepsy affects working memory performance is unclear but evidence suggest disruptions in the WM network [52]. MEG studies to examine the hemispheric lateralization of visuospatial memory circuitry prior to epilepsy surgery are severely lacking especially in children [53]. Importantly, visuospatial memory reorganization with seizure foci from the left and right hemispheres has not been investigated in detail. Although a significant role for the mesial temporal structure is suspected in visual-spatial memory, technological advances in MEG sufficient to detect hippocampal dynamics has become possible only recently [41]. Importantly, cortical stimulation and the Wada procedure cannot identify memory-specific circuitry or language circuit interactions whose activity patterns are developing in a non-typical brain environment due to on-going epileptic activity. Moreover, both cortical stimulation and the Wada are intimately related to the narrow time window and not suitable for delineation of neural pathways during complex tasks, and the repetition of these procedures to detect reliability cannot be performed.

Title: Pediatric Language and Memory Mapping in Refractory Epilepsy using Magnetoencephalography

PI: [name]

Site: Arkansas Children's Hospital

Several tasks exist to assess memory such as n-back task, the Sternberg Item Recognition task and others [54]. Some of these tasks require extended periods of time to complete the test or require verbal knowledge, which may impede the subject's ability to complete the test due to age or education. Our project proposes the use of an established working memory task that is an n-back paradigm that has been widely used to investigate working memory processes in neuroimaging research in children [55] and it is a simple task that kids can perform [56-59]. An n-back task consist of the presentation to participants with a sequence of stimuli and asked to answer when a stimulus matches another stimulus "n" trials back. Previous studies in memory assessment has shown extensively that n-back tasks are able to find memory disruptions in children [60-63] and some studies have noted particular aspects of memory to be more at risk. For example, Hershey et al. [61] shows that children with epilepsy scored lower than normative scores on measures of spatial tasks with high memory load or long delays, but not on short delay memory tasks which were within the normal range. Lindgren et al [62] showed that the percentage of children with epilepsy scored lower on visuospatial memory and learning (4%). Children with epilepsy appear to be at significant risk for memory impairment. It is not clear what particular aspects of memory are more likely to be affected or whether particular syndromes are more likely to be associated with particular impairments. Further research is needed to identify the extent and nature of the difficulties in children with epilepsy.

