The symbols and grid plane will be white on a black background. The type font will be Arial with 80pp size. Each trial will begin with a central fixation cross-displayed for 300 ms, followed by encoding, maintenance, and retrieval phases. The symbols and grid will appear for 1 s (encoding phase), then a blank inter-stimulus interval (ISI) will display for 1.5 s (maintenance phase). Next, the symbols and grid will appear for 1 s (retrieval phase). The subject will be tasked with indicating whether the encoding stimulus matched the retrieval stimulus using two buttons; one for "congruent" and the other for "incongruent" response. Button type will be counterbalanced among subjects. The task will take around 16 minutes. The visual stimuli will be projected through an LCD projector onto a white screen located about 0.5 m in front of the subject and subtending 1.0-4.0 and 0.5 degrees of horizontal and vertical visual angle, respectively. A MEG compatible keyboard will be used to measure the subject's responses for "congruent" and "incongruent". The subject will practice the memory task before going to the MEG system using a computer from MEG laboratory. This practice phase will consist of a short version of the memory task with duration of approximately 4 minutes.

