## **Data Analysis**

### ***Preprocessing***

MEG data will be exported for further analysis from the acquisition computer to the signal processing research software, Brainstorm [66] (<https://neuroimage.usc.edu/brainstorm/>), which is an open-source application dedicated to the analysis of brain recordings. Next, data will band-pass filtered between 0.5Hz to 100Hz and a notch filter will be applied for power-line noise removal (60Hz, 2nd order IIR notch filter with zero-phase lag). We will perform visual inspection to mark bad channels and segments. Data will be preprocessed for eye-blink and electrocardiogram reduction using a signal-space projection (SSP) technique [67]. The corresponding triggers recorded during acquisition will be used to import MEG epochs in the time window ranging from -200s to +800s with respect to the trigger [68, 69]. Baseline correction will be applied on the 200s before the trigger. Next, we will average across epochs to obtain an ERF waveform per subject for the language and memory tasks. Resting state data will use for baseline source imaging.

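### Memory-task responses are recorded but never used, so guessed and remembered trials carry equal weight in the memory waveform and nothing shows that the task was performed

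*Combined protocol and SAP*

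**What the plan says.** All references are to the combined protocol and SAP.

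**Task and responses (Memory Task).** "Each trial will begin with a central fixation cross-displayed for 300 ms, followed by encoding, maintenance, and retrieval phases". The grid is shown for 1 s, the screen is blank for 1.5 s, and a second grid is shown for 1 s. The subject is tasked with "indicating whether the encoding stimulus matched the retrieval stimulus using two buttons". Load is low or high according to the number and type of symbols. There are 24 stimuli in each of four load-by-congruency cells, 96 in all. The responses are captured: "A MEG compatible keyboard will be used to measure the subject's responses".

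**Averaging (Data Analysis, Preprocessing).** Bad channels and segments are marked by visual inspection, and eye-blink and cardiac artifacts are reduced. Then "we will average across epochs to obtain an ERF waveform per subject for the language and memory tasks". No rule refers to the response given.

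**Index and reporting (Statistical Analysis).** Memory dominance is the difference in activation between the hemispheres. MEG and clinical parameters are summarized descriptively. Accuracy, reaction time and load are not mentioned.

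**Rationale (Background and Rationale).** "Our project proposes the use of an established working memory task that is an n-back paradigm". In that paradigm, participants are "asked to answer when a stimulus matches another stimulus 'n' trials back". The supporting statements include "it is a simple task that kids can perform [56-59" and "n-back tasks are able to find memory disruptions in children [60-63".

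**The concern.** Aim 1 is the feasibility of measuring language and memory function with MEG. A recording completed without technical failure is not yet a measurement of memory. The child must also have held the first grid in mind, and the button response is the only evidence in the plan that this happened. Without it, a subject who pressed at random for the whole task yields a memory waveform and a dominance index that look as legitimate as anyone else's.

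Among children who do attempt the task, the averaged field mixes trials with and without successful memory, in proportions that differ from child to child. Differences in the index between subjects would then partly reflect how well each performed.

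The plan's own background makes the check by load more pressing. It reports, from one cited study, that children with epilepsy did worse on spatial tasks with high load or long delays but not on short-delay tasks. The maintenance interval here is 1.5 s. The documents do not say what counts as short, so whether this task taxes memory may depend on the load manipulation, which the analysis never examines.

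**Working it through.** The plan gives no figure on this point, so there is none to reproduce. The size is illustrated under stated assumptions.

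**Inputs from the documents (Memory Task).** Two response options; half the stimuli congruent and half incongruent within each load (24 and 24); 4 × 24 = 96 stimuli. Because the cells are balanced, random pressing or always pressing one button gives 50% expected accuracy overall and within each load.

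**Assumptions.** A share p of trials is truly remembered and answered correctly. The remaining 1 − p are guessed, half of them correctly. The documents give no value for p, so a range is shown.

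**Formulas.**
- Expected accuracy: p + (1 − p)/2 = (1 + p)/2
- Share without successful memory, all trials: 1 − p
- Share without successful memory, correct trials only: [(1 − p)/2] / [(1 + p)/2] = (1 − p)/(1 + p)

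| p | Accuracy | Non-memory share, all trials | Non-memory share, correct trials |
|---|---|---|---|
| 0.4 | 0.4 + 0.3 = 70% | 60% | 0.6/1.4 = 43% |
| 0.6 | 0.6 + 0.2 = 80% | 40% | 0.4/1.6 = 25% |
| 0.8 | 0.8 + 0.1 = 90% | 20% | 0.2/1.8 = 11% |

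At p = 0 (pure guessing) both shares are 100%. Correct-trial averaging cannot rescue that case; only reporting accuracy exposes it. Both parts of the fix are therefore needed.

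**Does losing epochs cancel the gain?** Suppose noise is independent and equal across epochs, and guessed epochs carry no memory signal. Signal-to-noise is then proportional to the memory share times the square root of the number of epochs.
- All N trials: p√N
- Correct trials: [2p/(1 + p)] × √[N(1 + p)/2] = p√N / √[(1 + p)/2]
- Ratio, correct to all: 1/√[(1 + p)/2], which is 1.20 at p = 0.4, 1.12 at p = 0.6 and 1.05 at p = 0.8

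The ratio exceeds 1 for every p below 1, so under this model the purer average outweighs the lost epochs. If each of the 96 stimuli is one trial, the expected correct epochs are 96 × 0.70 = 67, 96 × 0.80 = 77 and 96 × 0.90 = 86.

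**Can accuracy be read for one child?** At chance, the standard error of accuracy over 96 trials is √(0.25/96) = 5.1 percentage points. If 96 counts single displays, there are 48 trials and it is √(0.25/48) = 7.2 points. Either is precise enough for a descriptive comparison of 70% with 50%.

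**The label.** By the plan's definition, n-back compares a stimulus with one shown n trials earlier. In Memory Task, both grids belong to the same trial, no n is set or varied, and load comes from visual complexity. Calling it a 1-back does not help, because nothing is compared across trials.

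**The case against.** **The averaging rule is read from silence.** Preprocessing neither includes nor excludes error trials in so many words, and the analyst might drop them. That is fair, but the stated rule averages across epochs and the only rejection described is by signal quality. As written, errors stay in.

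**The size is hypothetical.** No remembered share appears in the documents, and all-or-none memory with pure guessing is a simplification. This stands, which is why a range is shown. A reader might also infer that guessed trials push the index toward one hemisphere. Nothing here shows that: the arithmetic shows dilution only. It also applies to the averaged field. The later selection of sources at 3.2 nAm or more is not linear, so the effect on the index could be larger or smaller.

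**A pilot should not carry confirmatory task checks.** This is a descriptive study of ten children (Study Design and Procedures) or fifteen (Study Population), and correct-only averaging cuts into 24 stimuli per cell and leaves unequal epoch counts. The point about pass/fail criteria is accepted: accuracy should be reported, not used as a test. The loss of epochs is a real but modest cost.

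**The n-back label might seem the larger fault.** A reader might infer that the study's conclusions rest on n-back validation that does not apply. The documents do not support that. Background and Rationale describes only the language protocol as validated. Risks and Benefits calls the memory task experimental and keeps its data out of presurgical planning. The memory index cites reference 68, not the n-back literature. References 56-59 have titles naming spatial or visuospatial working memory, paired symbols, or distraction, so they may support the task actually specified. Only reference 55 and the sentence citing references 60-63 are clearly tied to n-back.

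**Conclusion.** The plan collects the one piece of evidence that could show the memory task was performed, and then does not use it. In consequence the memory waveform and the dominance index weight guessed and remembered trials alike, and Aim 1 cannot tell a child who did the task from one who pressed at random.

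Under two-choice guessing with p between 0.4 and 0.8, 60% to 20% of the averaged epochs would lack successful memory, and averaging correct trials would reduce this to 43% to 11%. These figures rest on the assumed p and on all-or-none memory.

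The point is a minor but inexpensive improvement. The n-back label is a secondary wording matter: correcting it changes no planned analysis or result.

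**What to change.** 1. **Preprocessing.** Define the memory waveform as the average of artifact-free, correctly answered trials. Keep the all-trial average as a sensitivity analysis where correct epochs are few, and report the number of epochs behind each average.
2. **Statistical Analysis.** Report accuracy and reaction time by load, and each subject's accuracy beside 50% chance, as description and not as a pass/fail test. State the feasibility finding for memory with these figures in view.
3. **Background and Rationale (wording).** Reconcile the n-back label with the within-trial match in Memory Task. Either cite support for that task, or explain why reference 55 and the sentence citing references 60-63 apply to it.

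The cost is a few lines of text and a small analysis of responses already recorded. The downside is fewer epochs, and so a noisier average, in poor performers; correct-trial averaging also reduces guesses without removing them. The rule should be written before any memory results are seen.
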